9. STATISTICAL CONSIDERATIONS

9.1 STATISTICAL HYPOTHESES

Not applicable

9.2 SAMPLE SIZE DETERMINATION

Part I will enroll up to approximately 5 participants. The sample size is determined by the dose-increment steps implemented in this part.

In Part II, it is anticipated that a maximum of approximately 60 participants will be enrolled in each dose-escalation phase (IV and SC) (up to approximately 75 participants if one or several cohorts are expanded). *In case the OBD dose cohort is expanded both with and without obinutuzumab, an additional 15 participants may be enrolled.*

The probability of observing at least one event out of 15 participants for a true underline rate of 10% is 79% while out of 5 patients is 41%. Probabilities of the occurrence of 1 or more events for different ranges of true underline rates and different participant numbers are summarized in [Table 20](#).

The exact sample size for the dose-escalation part cannot be pre-determined and depends on the number of cohorts needed to reach the MTD (or highest safe dose if MTD is not reached).

Table 20 Probabilities for Observing Adverse Events

Total N of Participants	True AE Probability	Probability that AE ≥ 1	Probability that AE ≥ 2	Probability that AE ≥ 3
15	0.1	0.79	0.45	0.18
	0.2	0.96	0.83	0.60
	0.3	1.00	0.96	0.87
	0.4	1.00	0.99	0.97
	0.5	1.00	1.00	1.00
10	0.1	0.65	0.26	0.07
	0.2	0.89	0.62	0.32
	0.3	0.97	0.85	0.62
	0.4	0.99	0.95	0.83
	0.5	1.00	0.99	0.95
5	0.1	0.41	0.08	0.01
	0.2	0.67	0.26	0.06
	0.3	0.83	0.47	0.16
	0.4	0.92	0.66	0.32
	0.5	0.97	0.81	0.50

9.3 POPULATIONS FOR ANALYSES

For purposes of analysis, the following populations are defined in [Table 21](#).

Table 21 Analysis Populations

Population	Description
Efficacy	All participants who received at least one dose of RO7172508.
Safety	All participants enrolled in the study who received at least one dose of study treatment (RO7172508 and/or obinutuzumab if applicable) will be included in the safety population. Unless otherwise specified, the safety population will be the default analysis set used for all analyses.
DLT evaluable	DLT-evaluable participants are those who have completed the DLT window without a DLT, or participants who reported with a DLT. This population will be used in the determination of the MTD.
Pharmacokinetic	All participants who have received at least one dose of study treatment and who have data from at least one post-dose sample will be included in the PK analysis population. Participants will be excluded from the PK analysis population if they significantly violate the inclusion or exclusion criteria, deviate significantly from the protocol, or if data are unavailable or incomplete which may influence the PK analysis. Excluded cases will be documented together with the reason for exclusion. All decisions on exclusions from the analysis will be made prior to database closure.
Immunogenicity	Participants who had at least one pre-dose and one post-dose ADA assessment will be included and analyzed according to the treatment they actually received. The relationship between ADA status and safety, efficacy, PK, and biomarker endpoints will be analyzed and reported descriptively via subgroup analyses.

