During the course of this study, the need for obinutuzumab pretreatment will be assessed based on loss of RO7172508 exposure and/or ADA-related safety events. Details, including decision criteria, are provided in Section 4.1.3 and Appendix 9. If on-target toxicity is reported predominantly in the first cycle of treatment, fractionated dosing may be implemented for the first cycle to improve tolerability. RO7172508 treatment would start with 10% of the planned dose on Cycle 1 Day 1, 30% of the planned dose on Cycle 1 Day 8 and 60% of the planned target dose on Cycle 1 Day 15, followed by the full dose treatment from Cycle 2 Day 1 onwards as described in Figure 2. By using a step-up fractionated dosing approach, it is predicted that the lower peak exposures (C_{max}) will result in lower cytokine levels to that when the full dose is given on Day 1. The fractionated dosing regimen may be adjusted depending on emerging data and in discussion with the Investigators. A similar approach to increase the dose administered during the first three weeks as applied with dose-fractionation in the Q3W treatment group, may also be employed in the once weekly (QW) treatment group. If a patient in the fractionated dose cohort experiences any adverse event that results in a delay of the next administration of RO7172508 beyond one week, the dose at which the treatment should be restarted will require agreement between the investigator and the Sponsor.

Figure 2 Fractionated Dosing Design for Q3W and QW

At least 3 evaluable participants will be treated in each cohort during the IV or SC dose-escalation regimen.

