For each cohort, all participants will be followed through a 3-week DLT window (i.e., 21 days *after the first dose of RO7172508*). If fractionated dosing is implemented in Cycle 1 to improve tolerability, the DLT window will be extended to include the cycle where the planned target dose is administered in full i.e., *Cycle 1 Day 1 until the end of Cycle 2*. The DLT window will therefore be 6 weeks (42 days), or 8 weeks (56 days) if treatment has been delayed for no more than 14 days.

A new cohort can be opened when at least 3 evaluable participants of the previous cohort have completed the DLT window. *At least 3 evaluable participants must have a baseline sCEA level of ≤ 20 ng/ml.* If participants experience a DLT before completion of the last day of their DLT window, they will be considered as having completed their DLT window. Prior to opening a new cohort, the logistic regression model will be updated with the treatment outcome (i.e., the occurrence of DLT) and a new estimate of the MTD will be derived.

Enrollment into the next cohort will only resume after the Sponsor and the Investigators have jointly decided on the next dose-escalation step. Subject to clinical judgment, a new cohort of participants will be dosed at the new estimate of the MTD or the highest allowable dose based on pre-specified safety constraints as described below, whichever is lower and as guided by the mCRM-EWOC model. The design will continue as described, assigning participants to the MTD as estimated from all of the DLT data cumulatively, until one of the pre-defined stopping criteria is satisfied (see Section 4.1.4) or the pre-determined sample size of 60 DLT-evaluable participants is reached, whichever comes first. *Depending on emerging PK and safety data, the dose escalation may be evaluated taking into account sCEA levels at baseline in a sensitivity analysis (i.e. dose escalating more conservatively in the event toxicity is associated with low baseline sCEA levels).*

Built-in safety constraints are in place to prevent exposing participants to undue risk of toxicity, i.e., for Q3W dosing schedule, maximum allowable dose-increment, in absence of DLT, will be a maximum of 100%; if one DLT occurs then, an increment of 50% maximum will be allowed. The maximum dose that could be assessed in Part II will be 400 mg IV (see Section 4.3).

Provisional dose-levels in absence of DLT are listed in [Table 9](#).

Table 9 Provisional Dose Levels in Absence of DLT

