Dose Level	Dose (mg)	Dose-Increment if no DLT (%)	Next Dose if no DLT (mg)
1	1.6	100	3.2
2	3.2	97	6.3
3	6.3	90	12
4	12	67	20
5	20	100	40
6	40	100	80
7	80	88	150
8	150	100	300
9	300	33	400
10	400	N/A	N/A

Dose-frequency may be adjusted depending on the emerging PK data for RO7172508 and given an appropriate previously observed safety and tolerability profile. Different dosing schedules (e.g., non-fractionated and/or fractionated dosing) may be tested in parallel. If a decision is made to adjust the dosing schedule during the course of dose-escalation, the mCRM-EWOC algorithm will be updated with the available participant data and adapted to account for any difference in exposure of the new schedule. The initial starting-dose will not exceed a dose already tested and considered safe. Safety and DLT window may also be adapted. If fractionated dosing is implemented, the DLT window will be extended until the end of the cycle in which the planned full dose is administered.

- Dose-escalation to SC MTD

Once an MTD or OBD has been defined, or relevant clinical activity is seen (e.g., PR or better according to RECIST) for IV route of administration and schedule, SC administration will be tested. The starting dose *and regimen* for SC will be proposed based on the evaluation of the safety and efficacy data observed following IV administration; however, due to practical considerations, a minimum dose of 2 mg is defined for a single SC administration (Section 4.3).

In the QW cohorts, RO7172508 will be administered *three times per cycle (i.e. QW)*, with a maximum starting-dose of one third of the RO7172508 IV MTD dose or, in case MTD has not been reached, of the highest safe dose ≥ 6 mg tested in the IV dose-escalation part. *For a Q3W regimen the starting dose will not exceed the highest safe dose tested in the IV Q3W dose escalation.*

The maximum allowed dose will be 160 mg QW *or* 400 mg Q3W (flat dose). Different dosing schedules (e.g., non-fractionated and/or fractionated dosing) may be tested.

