7.1 DISCONTINUATION OF STUDY TREATMENT

See the SoA (Section [1.3](#) for data to be collected at the time of treatment discontinuation and follow-up and for any further evaluations that need to be completed.

Participant must discontinue study treatment if they experience any of the following:

- Pregnancy
- Grade 3 IRR/CRS for RO7172508
- IgE-mediated hypersensitivity reactions, including anaphylaxis.
- Any toxicity which is not manageable with dose-delays (as allowed per protocol), dose-decrease and/or appropriate treatment.
- Symptomatic disease progression when there is a consensus that the participant will not benefit from study treatment.
- If a patient develops alanine aminotransferase or aspartate aminotransferase increase > 10x ULN associated with the 3rd infusion of RO7172508 or later.

Participants who discontinue study treatment prematurely will be asked to return to the clinic for an End-of-Treatment visit (see Section [8.10.3](#)) and may undergo follow-up assessments (see Section [8.10.4](#)). The primary reason for premature study treatment discontinuation should be documented on the appropriate eCRF. Participants who discontinue study treatment prematurely may be replaced for the following reasons to ensure adequate numbers of evaluable participants:

- Participant who withdraws from the study prior to the treatment start may be replaced.
- Participants who fail to complete their DLT assessment period because of non-drug-related reasons.
- In the case of a major protocol violation when participants are excluded from Cycle 1 of treatment (these participants will be excluded from the MTD/DLT analysis

but might continue the treatment if deemed beneficial and according to clinical judgment).

- Cohorts may be expanded to acquire additional paired tumor biopsies.

Participants will be treated for 24 months (the treatment period may be modified if supported by emerging data) or until disease progression, loss of clinical benefit, unacceptable toxicities, or withdrawal from treatment for other reasons or death.

As with other immunotherapies, treatment beyond RECIST ([Appendix 6](#)) progression could be considered. The criteria below will be needed to continue treatment beyond initial apparent progressive disease per RECIST v1.1 (e.g., radiological progression secondary to tumor inflammation):

- Absence of clinical deterioration and Investigator–assessed potential clinical benefit for the participant and

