7.1.1 Temporary Interruption

If an IRR/CRS develops, the infusion of RO7172508 should be slowed down or interrupted. The participant should be monitored until complete resolution of the symptoms and treated as clinically indicated. Treatment or concomitant medication may include acetaminophen/paracetamol, antihistamine, IV saline, oxygen, bronchodilators, corticosteroids, and vasopressors, depending on the symptoms (see Section [8.3.8.1](#)). Study treatment should be re-started as soon as medically justified in the opinion of the Investigator.

The infusion may be resumed at $\leq 50\%$ (Grade 1 IRR/CRS) or $\leq 25\%$ (Grade 2 IRR/CRS) of the previous rate. The infusion can be re-escalated to the initial rate if study treatment is considered well-tolerated after one hour of infusion.

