
Grade 2 Hypotension: responds to fluids
 
OR
 
Hypoxia*: requires <40% FiO₂ (or ≤5 L/min of 100% O₂) to maintain adequate hemoglobin oxygen saturation
	
 – Follow all Grade 1 recommendations – Hold further RO7172508 treatment until symptoms completely resolved – At the restart of the infusion, slow down the rate of infusion to 25% of original rate – If event occurred during infusion, and symptoms recur with the same or greater severity following interruption of RO7172508 infusion, the infusion must be stopped immediately. Consider to manage as a Grade 3 event. No further RO7172508 will be administered for the cycle – Monitor cardiac and other organ functions closely – Hemodynamic support as indicated and oxygen for hypoxia – Admit to ICU as appropriate – Consider administering a single dose of tocilizumab IV 8 mg/kg – If no improvement within 24 hours: 
 a) Notify Medical Monitor b) Administer IV corticosteroids (e.g., methylprednisolone [2 mg/kg/day] or dexamethasone 10 mg if neurologic symptoms are present) – Additional monitoring and evaluation: 
 – Consider 24 hour hospitalization – Work up for organ functions (e.g. liver, cardiac) based on clinical assessment of the Investigator – May receive RO7172508 in next cycle if symptoms resolve to Grade ≤1 with the approval of the Medical Monitor including considerations for dose reduction and/or reduction of infusion rate at the next administration. – At next cycle administer pre-medications that may include antihistamine, antipyretics/NSAIDs, antiemetic, and corticosteroids

Table 17 Recommendations for Management of IRRs and CRS considered related to RO7172508^a (cont.)

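### DLT evaluability carries no minimum-dose condition, so partly dosed participants can enter the MTD model as DLT-free and the MTD can be biased upward

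*Combined protocol and SAP*

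**What the plan says.** **The set.** Section 9.3, Table 21: "DLT-evaluable participants are those who have completed the DLT window without a DLT, or participants who reported with a DLT". The entry continues: "This population will be used in the determination of the MTD". Nothing in it refers to dose received.

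**The window.** Section 4.1.2.2: "For each cohort, all participants will be followed through a 3-week DLT window", counted as 21 days from the first dose. SC escalation uses the same window unless updated on emerging data. For fractionated dosing: "If fractionated dosing is implemented, the DLT window will be extended until the end of the cycle in which the planned full dose is administered", which the section works out as 42 days, or 56 with a delay of up to 14 days.

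**Protocol actions that reduce the dose.** Table 17 (Section 8.3.8.1) stops the infusion if a Grade 2 reaction recurs at the same or greater severity after an interruption, and then: "No further RO7172508 will be administered for the cycle". Tables 18 and 19 hold treatment for Grade 2 tumor-inflammation events and Grade 2 diarrhea until they improve to Grade 1 or lower.

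**What counts as a DLT.** Under Section 4.1.3.1 non-hematological toxicity must be Grade 3 or higher, with listed exceptions. A dose delay from RO7172508-related toxicity is a DLT only when it exceeds 14 days.

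**Non-completers.** Section 7.1 lists as replaceable: "Participants who fail to complete their DLT assessment period because of non-drug-related reasons". Section 7.2 says that participants who withdraw for safety reasons are not replaced.

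**The model.** Appendix 8, Section 1.2, relates DLT probability to dose without saying whether this is the planned or the received dose.

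**The concern.** A DLT-free outcome is evidence that the assigned dose is tolerable only if something close to that dose was given. Table 21 does not ask for this, and the protocol itself directs actions that leave some participants short. Because these actions follow the protocol, the exclusion for major protocol violations in Section 7.1 does not reach them, and neither does the radiotherapy rule in Section 6.5.1.1. Infusion stops and withheld doses are likely to become more common as the dose approaches the MTD, so any understatement of the DLT rate would fall where the MTD is chosen. The MTD is a primary objective of this first-in-human study, and Table 23 reports its model estimate with a 90% credible interval.

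There is a second, separate gap. A participant who leaves follow-up before the window ends for a drug-related reason, without a DLT, is outside Table 21, and the replacement rules do not say how that participant is handled.

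**Working it through.** **1. Can a partly dosed participant be DLT-free under the rules?**

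- *Unfractionated IV Q3W.* The window contains one infusion. A recurrent Grade 2 IRR/CRS ends it. Grade 2 is not a DLT, and 21 days of follow-up complete the window. The participant is evaluable and DLT-free.
- *SC QW.* Doses are planned on Days 1, 8 and 15. A Day 8 dose held for Grade 2 toxicity and delayed by exactly 14 days falls on Day 8 + 14 = Day 22. The delay does not exceed 14 days, so it is not a DLT. One of three planned doses may have been given when the 21 days have run.
- *Fractionated.* The window runs to the end of the full-dose cycle. This implies that the full dose was given, but Table 21 does not state it.

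**2. Reproduce the plan's own figure.** Appendix 8, Table 2, Scenario 1 has alpha = -0.11, beta = 1.74 and reference dose 100 mg:

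p(d) = expit(-0.11 + 1.74 ln(d/100)), so d = 100 exp((logit p + 0.11)/1.74).

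- p = 0.20: logit = -1.386, d = 48.0 mg.
- p = 0.35: logit = -0.619, d = 74.64 mg.

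The appendix states 48-75 mg and a true MTD of 74.64 mg. Both agree. At half the MTD, about 37.5 mg, p is 14%.

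**3. Effect of half-dosing.** Assumptions, not in the documents: a share f receives half the dose, has the DLT risk of that half dose, and is entered at the assigned dose. The dose that appears to have a 35% rate solves

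(1 - f) p(d) + f p(d/2) = 0.35.

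| f | apparent 35% dose | true rate there | check |
|---|---|---|---|
| 0 | 74.6 mg | 35% | |
| 0.10 | 79 mg | 37% | 0.90 × 0.372 + 0.10 × 0.151 = 0.350 |
| 0.20 | 84 mg | 40% | 0.80 × 0.397 + 0.20 × 0.164 = 0.350 |
| 0.33 | 91 mg | 43% | 0.67 × 0.432 + 0.33 × 0.185 = 0.350 |

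The shifts from 74.6 mg are about 6%, 12% and 22%.

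**4. Effect through the design.** The escalation was rebuilt from Appendix 8 (10/90 mixture prior, dose grid, increment limits, stopping rule, cohorts of 3, start at 0.5 mg), with 500 simulated trials per setting. With no partial dosing, Scenario 1 gives a mean selected MTD of 74.7 mg (10-90% quantiles 44.5 and 102), against the stated 72.3 mg (44.5, 100).

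| share half-dosed | mean selected MTD | P(selected > true MTD) |
|---|---|---|
| 0 | 74.7 mg | 0.42 |
| 10% | 77.2 mg | 0.46 |
| 20% | 82.1 mg | 0.51 |
| 30% | 86.0 mg | 0.58 |

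The simulation standard error of each probability is about sqrt(0.42 × 0.58/500) = 0.022, so the 10% row alone is not clearly separated from the baseline. The trend across rows is. In an extreme case (30% receiving one-tenth of the dose) the mean is 102.9 mg. Excluding and replacing partly dosed DLT-free participants brings it back to 71.5 mg.

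**5. Direction of the early-leaver gap.** Take a cohort of 3 at 40 mg, no earlier DLTs, one DLT in the cohort and one further participant in question:

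- counted DLT-free (1/3): next dose 60 mg, overdose probability 0.118;
- excluded (1/2): next dose 60 mg, overdose probability 0.153;
- counted as a DLT (2/3): next dose 50 mg.

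Dropping the participant is less cautious than counting a DLT, but slightly more cautious than counting DLT-free.

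**The case against.** The case against is substantial, and several parts of it stand.

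- **The IV route is narrow.** Section 7.1.1 says "If an IRR/CRS develops, the infusion of RO7172508 should be slowed down or interrupted", but that is a temporary measure with restart intended, and it lowers the infusion rate rather than the dose. Only a recurrence after interruption ends dosing, and Table 17 then suggests considering management as a Grade 3 event. This limits how often the route arises. It does not make the event a DLT.
- **Fractionated cohorts.** Section 4.1 says "RO7172508 treatment would start with 10% of the planned dose on Cycle 1 Day 1", and a reader might infer that someone given only that step can complete the window DLT-free. The documents do not support this. The window runs to the end of the full-dose cycle, and a related delay of more than 14 days is itself a DLT. What remains is that the full-dose requirement is implied, not written.
- **Drug-related stops.** A reader might also infer that these are dropped from the MTD set. Stopping drug is not leaving the window: participants are followed through it, and most Grade 3 or higher non-hematological toxicity is already a DLT. Only those who leave follow-up early without a DLT fall outside Table 21.
- **Clinical review.** Section 4.1.5 has escalation decisions draw on all relevant available data, and Section 4.2.1 lets judgment override the model. A truncated infusion would probably be seen. That softens individual decisions but does not correct the reported model estimate.
- **Size.** No partial-dosing rate is documented. The 10% shift is less than one 5 mg grid step, and all three shifted doses lie inside Scenario 1's stated 10-90% range of 44.5-100 mg. That range is sampling spread, however, whereas partial dosing moves its center.

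**Conclusion.** The point holds as a gap in the evaluability rule. Table 21 admits partly dosed participants as DLT-free, and the protocol gives at least two ways to become one: a stopped IV infusion and withheld weekly SC doses. If they are entered at the assigned dose, the MTD can be biased upward. With 10% to 33% half-dosed in Scenario 1, the apparent 35% dose rises to 79-91 mg, at true rates of 37-43%. These figures depend on the assumed share, the assumed half dose, the Scenario 1 curve and entry at the planned dose.

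Two stronger conclusions do not follow. The documents do not establish that the MTD is biased upward, because they give neither the frequency of partial dosing nor the dose that enters the model. Nor do the missing dose condition and the loss of early leavers act together in one direction. They concern different participants, and the sign of the second depends on the alternative it is compared with. For early leavers with drug-related toxicity, what is established is that Table 21 and Sections 7.1 and 7.2 leave their handling unstated.

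**What to change.** 1. Amend Table 21 so that a participant without a DLT is evaluable only if a minimum share of the planned RO7172508 was received within the window. The sponsor should set and justify the share. For fractionated cohorts, state explicitly that the full dose must have been given.
2. Replace participants who fall below the minimum for reasons unrelated to the drug.
3. Do not silently drop participants who fall below it because of RO7172508-related toxicity, and do not count them as DLT-free at the full dose. Flag them, and add a sensitivity run of the model that counts them as DLTs.
4. State in Appendix 8 whether planned or received dose enters the model.
5. Reconcile Table 21 with Sections 7.1 and 7.2, including participants who leave follow-up early for drug-related reasons without a DLT.

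The cost is a short amendment to Table 21, Sections 7.1 and 7.2 and Appendix 8, possibly a few replacement participants, and one extra model run. If received dose is chosen, the model inputs also change, which is more than a wording edit.
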